9.3.3. Covariates and other population characteristics

Characteristics of the study population that are to be described will include calendar year of delivery, maternal age at conception, parity (number of live and still births prior to the on-study pregnancy); indication for AED use, marital/cohabiting status; pregravid body mass index (BMI) as recorded at the first antenatal visit or via a hospital diagnosis of obesity; smoking during pregnancy as recorded at the first antenatal visit; single or multiple gestation; Caesarean delivery; and child's sex. Caesarean delivery and child's sex will be reported but will not be used for adjustment. Indication for gabapentin (and other AEDs) use in 12-months pre-LMP (epilepsy, neuropathic pain, 'other' indications) will be reported

descriptively but will not be used for adjustment as administrative data available for this study have low sensitivity in identifying relevant indications for all pregnancies.

[figure not shown]
The covariates to be included in the propensity-score model are:

- calendar year of delivery;
- maternal age in years at conception;
- marital/cohabiting status;
- smoking during pregnancy;
- obesity (BMI \geq 30 kg/m²) or a hospital diagnosis of obesity;
- single or multiple gestation;
- hospital-recorded morbidity based on inpatient and outpatient specialist care or proxy medication use in 12 months pre-LMP: migraine or other headache syndromes, other neurologic disorders, depression, bipolar disorder, alcohol abuse or dependence, drug abuse or dependence, hypertension, haematological diseases, diabetes, asthma, liver diseases, renal impairment, rheumatic diseases, obesity, disorders of female pelvic organs/genital tract, thyroid disorders, infections (infections will be assessed in 90 days pre-LMP). In Finland, in addition to the hospital diagnoses, diagnoses from primary care are also available and will be used;
- indicators of maternal health care utilisation in the 12 months pre-LMP (number of inpatient and specialised outpatient encounters);
- for the outcome congenital malformations: maternal medication use each as a dichotomous variable, defined by at least one dispensing during the first trimester (AEDs, antidepressants, hypnotics, antipsychotics, analgesics, antihypertensives, non-steroidal anti-inflammatory drugs, drugs for peptic ulcer/gastroesophageal reflux, folic acid, drugs for in-vitro fertilization, thyroid hormones, systemic corticosteroids, and anti-infectives for systemic use);
- for the outcomes other than congenital malformations: maternal medication use each as a dichotomous variable, defined by at least one dispensing during any trimester (AEDs, antidepressants, hypnotics, antipsychotics, analgesics, antihypertensives, non-steroidal anti-inflammatory drugs, drugs for peptic ulcer/gastroesophageal reflux, folic acid, drugs for in-vitro fertilization, thyroid hormones, systemic corticosteroids, and anti-infectives for systemic use).

[figure not shown]
Full list of the study variables and their operational definitions are provided in [Annex 3](#).

Figure 2. Examples of follow up period for neurodevelopmental outcomes during the study period

[figure not shown]
1.

2.

3.

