9.4. Data sources

Data sources used to construct the analysis dataset for this study are presented in [Table 2](#). Within each country, records from all registries are linkable at the individual level by a unique national person identifier. For births recorded in the birth registries, a maternal unique identifier is a variable on the record of the offspring, enabling exact linkage between a given offspring and maternal history of medication dispensing or diagnoses before or during pregnancy.

Diagnoses in all countries are registered based on the ICD-10 coding system and accessed through registers as specified in [Table 3](#). Similarly, medications are classified according to the ATC coding system and accessed through prescription registers. The medical birth registers in the included countries furthermore contain similar information on other relevant covariates (calendar year of delivery, maternal age at conception, parity; marital/cohabiting status; pregravid body mass index (BMI); smoking during pregnancy; single or multiple pregnancy; and child's sex.)

Validity of routine data in Nordic national registries has been found to be high in all countries.¹⁷⁻²⁶ In Denmark, positive predictive value of diagnoses of cardiac malformations is 89%.²⁷ For drugs used chronically, there is also high level of agreement between general practitioner and dispensing records.²⁸ An agreement between dispensing records and drug use reported in the standard medical antenatal records included in the birth register was 69% for antiepileptics in Sweden.²⁹

Table 2. National registries in Denmark, Finland, Norway and Sweden and type of data available from each registry

Study variable/role	Type of data	Data source(s)	Coding system(s) used
Person identification (mothers and children)	Unique personal identifier for data linkage	Danish Civil Registration System ³⁰ Danish Civil Registration System ³⁰ Finnish Medical Birth Register* National Registry of Norway Swedish Total Population Register ³¹	N/A
Study population	Pregnancies ending in singleton/multiple live birth or stillbirth	Danish Medical Birth Registry ²⁶ Finnish Medical Birth Register* ²⁶ Medical Birth Registry of Norway ²⁶ Swedish Medical Birth Register ²⁶	A specific variable in each birth registry

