9.7. Data analysis

For all data analyses, the birth (not the patient/mother) will be the unit of analysis. Given that a woman could have more than one birth during the study period, data analyses will account for correlated observations using GEE (generalized estimating equation) or robust variance estimates. All steps of the country-specific data analyses will be conducted separately in each participating country according to the description below. Each country will generate a set of identical analytic tables. Registry data will not be provided for very low numbers (less than 5 events) due to data security and data confidentiality rules.

After conducting the country-specific data analyses, country-specific datasets containing crude and adjusted estimates of association will be transferred to Aarhus University Hospital, Denmark, for meta-analyses.

Given that gabapentin has several indications and that administrative data available for this study have low sensitivity in identifying relevant indications for all pregnancies, in this study pregnancies exposed to gabapentin will be compared with pregnancies exposed to medications with similar sets of indications. Because confounding by indication or severity

of indication may persist even against an active comparator,⁷ the amount of confounding may be inferred indirectly by examining whether estimates of association differ depending on the comparator. Here, pregabalin and lamotrigine, which are both indicated for epilepsy, have been identified as suitable active comparators.

In a 2019 publication from Sweden, all individuals aged 15 years or older and being dispensed at least 2 prescriptions of gabapentin in the period 2006-2013 were identified (N=85,360).⁴⁹ The indication of use (i.e. health status before start of treatment) was 6.4% epilepsy, 20% psychiatric disorders, and 52.1% musculoskeletal disorders. In the same publication, the indication of use for pregabalin (n=120,664) was 5.4% epilepsy, 40.9% psychiatric disorders, and 46.2% musculoskeletal disorders. Published data on the most common gabapentin indication in pregnant women are unavailable at this time.

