9.7.3.1. Computation of propensity scores

To account for confounding by all measured covariates, adjusted analysis will be conducted using propensity score (PS) stratification, following the approach by Paterno et al.⁵⁰ For each pregnancy, a PS will be computed, using logistic regression, as the probability being exposed

to gabapentin vs. given comparator conditional on the measured covariates listed in [Section 9.3.3](#) and [Annex 3](#).⁵¹

PS will be estimated for each birth using a generic-outcome model, meaning that all prespecified covariates will be included in the PS-estimating model, regardless of the association with the outcome. Wyss et al showed, in a simulation study, that such a model performs well when multiple outcomes are being examined;⁵² furthermore, it is reasonable to assume in this study that all confounders distort the association in the same direction for all outcomes. In case of model non-convergence, covariates with the smallest cell counts (corresponding to the lowest prevalence of covariates) will be removed one-by-one until convergence is achieved. Categories of variables with small cell counts may be collapsed if applicable by an analyst in each country.

A separate PS will be estimated for each study population and comparison. To summarise, the following sets of propensity scores will be estimated:

1. First-trimester gabapentin (monotherapy or polytherapy) vs. first-trimester unexposed to AEDs
2. First-trimester gabapentin (monotherapy or polytherapy) vs. first-trimester pregabalin (monotherapy or polytherapy)
3. First-trimester gabapentin (monotherapy or polytherapy) vs. first-trimester lamotrigine (monotherapy or polytherapy)
4. First-trimester gabapentin (monotherapy or polytherapy) vs. first-trimester pregabalin or lamotrigine (monotherapy or polytherapy)
5. First trimester gabapentin (monotherapy only) vs. first-trimester unexposed to AEDs
6. First trimester gabapentin (monotherapy only) vs. first-trimester pregabalin (monotherapy only)
7. First trimester gabapentin (monotherapy only) vs. first-trimester lamotrigine (monotherapy only)
8. First-trimester gabapentin (monotherapy only) vs. first-trimester pregabalin or lamotrigine (monotherapy only)
9. Any-trimester gabapentin (monotherapy or polytherapy) vs. any-trimester unexposed to AEDs
10. Any-trimester gabapentin (monotherapy or polytherapy) vs. any-trimester pregabalin (monotherapy or polytherapy)

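### Parity is collected and called a relevant covariate but is left out of the propensity score without a reason; a sensitivity analysis adding recorded epilepsy is also worth pre-specifying for the two contrasts that involve lamotrigine.

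*Protocol*

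**What the plan says.** Protocol section 9.3.3 has two lists. The first gives characteristics to be described and includes "parity (number of live and still births prior to the on-study pregnancy); indication for AED use, marital/cohabiting status". The second is introduced by "The covariates to be included in the propensity-score model are" and names calendar year, maternal age, marital status, smoking, obesity, multiplicity, a set of hospital-recorded morbidities, health care use and dispensed medicines. Parity is not in it, nor in the matching list in the abstract (section 4).

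Between the two lists the section says which described variables stay out of the adjustment: "Caesarean delivery and child's sex will be reported but will not be used for adjustment". For indication (epilepsy, neuropathic pain, other) it adds a reason: "will not be used for adjustment as administrative data available for this study have low sensitivity in identifying relevant indications". It says nothing about parity.

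Two other places point the other way. Section 9.4 says that the birth registers "contain similar information on other relevant covariates (calendar year of delivery, maternal age at conception, parity; marital/cohabiting status" and further items. Section 9.7.3.1 opens with "To account for confounding by all measured covariates, adjusted analysis will be conducted using propensity score (PS) stratification", and defines the score by the covariates in section 9.3.3 and Annex 3.

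**The concern.** The protocol fixes the covariate list, so this is not detail left to a later analysis plan. As written, parity is measured everywhere, called relevant, tabulated and not adjusted for, while the text promises adjustment for everything measured. Because each country's analyst builds the score separately, one team could read section 9.3.3 as including parity and another as excluding it.

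If parity differs between gabapentin users and a comparator and is related to preterm birth, small for gestational age, low birth weight or stillbirth, avoidable bias stays in the primary adjusted ratios.

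The second, smaller issue is epilepsy. Section 9.9 says that epilepsy is associated with adverse pregnancy outcomes and that the indications for the comparator drugs may differ from those for gabapentin. Section 7 gives epilepsy as the only indication for lamotrigine. An unadjusted excess of epilepsy among lamotrigine users would raise risk in the comparator and make gabapentin look safer, which is the less cautious direction for a safety study.

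**Working it through.** **1. The plan's own figure.** Table 4 gives 1.465 as the upper limit that can be ruled out for any major malformation (3%), gabapentin against unexposed. The inputs are 1,743 exposed, 3,298,823 − 1,743 = 3,297,080 unexposed, true ratio 1, 95% interval and 80% probability.

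Limit = exp[(1.960 + 0.842) × √{(0.97/0.03) × (1/1,743 + 1/3,297,080)}] = exp(2.802 × 0.1362) = 1.465.

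The figure reproduces, as does 1.223 for a 10% outcome (preterm birth or small for gestational age). Both are crude calculations that use no covariates, so nothing below changes them. The issue is bias, not stated precision.

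**2. Bias formula.** If a binary confounder has prevalence p1 in gabapentin users and p0 in the comparator, and outcome ratio RR, the unadjusted ratio is multiplied by [1 + p1(RR − 1)] / [1 + p0(RR − 1)].

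**3. Parity.** The protocol gives no parity distribution and no parity–outcome ratio. Assumed: 45% nulliparous in the comparator, a gap of 3, 5 or 10 points either way, and RR 1.3, 1.5 or 2.0.

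| Gap | RR 1.3 | RR 1.5 | RR 2.0 |
|---|---|---|---|
| +3 / −3 points | 1.008 / 0.992 | 1.012 / 0.988 | 1.021 / 0.979 |
| +5 / −5 points | 1.013 / 0.987 | 1.020 / 0.980 | 1.034 / 0.966 |
| +10 / −10 points | 1.026 / 0.974 | 1.041 / 0.959 | 1.069 / 0.931 |

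Example: (1 + 0.55 × 1)/(1 + 0.45 × 1) = 1.069. The range is about 1% to 7%. At its top it is not trivial beside the tightest limit in the unexposed contrast: ln(1.069)/ln(1.223) = 0.33, a third of that margin on the log scale.

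**4. Epilepsy, by comparator.** Section 9.7 gives 6.4% for gabapentin and 5.4% for pregabalin, from Swedish users aged 15 or older with, for gabapentin, at least two dispensings; they are not figures for pregnant women. The rest is assumed: epilepsy–outcome RR 1.25 to 2.0, 0.5% to 1% epilepsy in the unexposed, and 30% to 80% in lamotrigine users. For the combined comparator the share is weighted by the any-time counts in Table 3 (8,584 lamotrigine, 2,930 pregabalin, overlap ignored). At 50% in lamotrigine users it is (8,584 × 0.50 + 2,930 × 0.054)/11,514 = 0.387.

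| Comparator | RR 1.25 | RR 1.5 | RR 2.0 |
|---|---|---|---|
| Pregabalin (5.4%) | 1.002 | 1.005 | 1.009 |
| Unexposed (1% to 0.5%) | 1.013–1.015 | 1.027–1.029 | 1.053–1.059 |
| Lamotrigine, 30% | 0.945 | 0.897 | 0.818 |
| Lamotrigine, 50% | 0.903 | 0.826 | 0.709 |
| Lamotrigine, 80% | 0.847 | 0.737 | 0.591 |
| Combined, lamotrigine share 50% | 0.926 | 0.865 | 0.767 |

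These factors assume that nothing already in the score stands in for epilepsy, so they are outer values.

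**5. Would an insensitive record help?** Take lamotrigine at 50% and RR 1.5 (factor 0.826). With sensitivity s and an assumed specificity of 1, epilepsy among comparator births without a record is 0.5(1 − s)/(1 − 0.5s). Standardise the comparator to the gabapentin record distribution. At s = 0.5 the recorded share in gabapentin users is 0.032 and unrecorded epilepsy in the comparator is 0.333. The expected comparator risk is 0.032 × 1.5 + 0.968 × (1 + 0.333 × 0.5) = 1.177, and the factor is 1.032/1.177 = 0.877. At s = 0.2, 0.3 and 0.8 it is 0.842, 0.852 and 0.934.

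**The case against.** The case for the plan is strongest on indication. The exclusion is stated and explained in section 9.3.3 and repeated as a limitation in section 9.9, which adds that the pilot data hold indication for only a minority of pregnancies. Section 9.7 gives the planned answer: active comparators, with residual confounding judged from whether estimates differ between them. With recording below half, the marker moves 0.83 to 0.88 at best in the example, so most of the assumed bias stays. The marker would also be sparse. Table 3 has 344 to 500 first-trimester gabapentin exposures per country, and at 6.4% epilepsy and 50% recording that is about 11 to 16 marked births. Section 9.7.3.1 drops the rarest covariates first if a model fails to converge. All of this stands, and it is why recorded epilepsy belongs in a sensitivity analysis and not in the primary score.

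The stated reason is still weak as a reason for never using the record. Section 9.9 says that hospital diagnoses are imperfect for covariates as well as for indications, yet other diagnoses are kept. It is fair to reply that the listed morbidities may also be found through proxy medicines, whereas for indication the obvious proxy is the exposure itself.

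On parity, the code list in Annex 3 is not in the text at hand and might name it. Adjusted variables such as maternal age and marital status may also carry part of its effect. That lowers the likely size, but it does not explain why section 9.3.3 gives a reason for leaving out indication and none for parity.

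A reader might infer that leaving indication out means no control for it. The documents do not support that. Other neurologic disorders, headache, depression, bipolar disorder, rheumatic diseases, antidepressants, antipsychotics, analgesics and anti-inflammatory drugs are all in the score. For the same reason the psychiatric shares in section 9.7 (20% for gabapentin, 40.9% for pregabalin) cannot be read as an unadjusted difference, and they do not establish a need for anxiety or pain terms.

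**Conclusion.** The parity point holds. The variable is measured, called relevant and omitted from a fixed list without a reason, and the list conflicts with the stated aim of the score. The cost of the omission is about 1% to 7% in the adjusted ratios, direction unknown, under the assumed nulliparity gaps and outcome ratios. The protocol supplies neither, so this is a range of plausible size, not an estimate.

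On indication only a limited point holds. A reader might infer that a known confounder was overlooked and must go into the primary score. The documents show a reasoned, disclosed choice. On the protocol's own shares the epilepsy effect against pregabalin is under 1%, and on assumed figures it is 1% to 6% against unexposed. It becomes material only where lamotrigine is in the comparator, and the size there rests on an epilepsy share that the protocol does not state. The direction, towards gabapentin looking safer, holds throughout the assumed range. The protocol names epilepsy, not neuropathic pain, as associated with the outcomes.

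**What to change.** 1. Add parity (0, 1, 2 or more) to all 16 propensity-score models, and to the covariate lists in the abstract and section 9.3.3. Reconcile section 9.3.3 with sections 9.4 and 9.7.3.1, so that the phrase on all measured covariates matches the list and its stated exceptions. The data are already held, and the cost is one three-level covariate per model.

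2. Keep indication out of the primary score. Pre-specify a sensitivity analysis that adds epilepsy recorded in the 12 months before the last menstrual period to the score for gabapentin against lamotrigine and against pregabalin or lamotrigine. State that it gives partial control only, because indication is recorded for a minority, and that a small shift does not show that confounding by epilepsy is absent. State also whether the category of other neurologic disorders includes epilepsy, since that would sit badly with the statement that indication is not used. The cost is sparse cells, some extra trimming where epilepsy separates the two drugs, and one more set of estimates per country.

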Characteristics of the study population that are to be described will include calendar year of delivery, maternal age at conception, parity (number of live and still births prior to the on-study pregnancy); indication for AED use, marital/cohabiting status; pregravid body mass index (BMI) as recorded at the first antenatal visit or via a hospital diagnosis of obesity; smoking during pregnancy as recorded at the first antenatal visit; single or multiple gestation; Caesarean delivery; and child's sex.

The covariates to be included in the propensity-score model are:

- calendar year of delivery;
- maternal age in years at conception;
- marital/cohabiting status;
- smoking during pregnancy;
- Obesity (BMI ≥ 30 kg/m²) or a hospital diagnosis of obesity;
- Single or multiple gestation;
- hospital-recorded morbidity;
- indicators of maternal health care utilisation in the 12 months pre-LMP (number of inpatient and specialised outpatient encounters);
- for congenital malformations outcome: maternal medication use, each as a dichotomous variable.

Data source: Data from national population-based administrative registries in Denmark, Finland, Norway, and Sweden will be used in this study. These national registries include patient, birth, prescription, and total population registries. Within each country, records from all registries are linkable at the individual level by a unique national person identifier. For births recorded in the birth registries, a maternal unique identifier is a variable on the record of the offspring, enabling exact linkage between a given offspring and maternal history of medication dispensing or diagnoses before or during pregnancy.

Study size: The study size is estimated at greater than 3,000,000 pregnancies, including approximately 1743 exposed to gabapentin at any time. A study of this size will rule out a relative risk with a 95% upper confidence limit of 1.5 with 80% probability, assuming the following: gabapentin vs. 'unexposed to AEDs' as comparator, background prevalence of major congenital malformations is 3%; gabapentin exposure prevalence is 0.8%; and the true underlying risk ratio is 1.0.

Data analyses:

For all data analyses, the birth (not the patient/mother) will be the unit of analysis. Given that a woman could have more than one birth during the study period, data analyses will account for correlated observations using GEE (generalized estimating equation) or robust variance

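### Pregravid BMI is to be described but enters the propensity score only as obesity yes/no, so differences below BMI 30 are neither directly adjusted for nor checked after weighting

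*Protocol*

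**What the plan says.** Section 9.3.3 of the protocol lists, among the characteristics to be described, "pregravid body mass index (BMI) as recorded at the first antenatal visit or via a hospital diagnosis of obesity". Section 9.4 introduces the register content with "The medical birth registers in the included countries furthermore contain similar information on other relevant covariates", and the list that follows includes "pregravid body mass index (BMI); smoking during pregnancy; single or multiple pregnancy; and child's sex".

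The propensity-score covariates are listed in the abstract and again in section 9.3.3. In both places the BMI term is "Obesity (BMI ≥ 30 kg/m²) or a hospital diagnosis of obesity" (abstract wording). In section 9.3.3 obesity appears a second time among the hospital-recorded morbidities: "renal impairment, rheumatic diseases, obesity, disorders of female pelvic organs/genital tract, thyroid disorders".

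Section 9.3.3 also names what is reported without being adjusted for. It says "Caesarean delivery and child's sex will be reported but will not be used for adjustment", and it treats indication the same way because the data identify it with low sensitivity. BMI is not among these exceptions, and no reason is given for cutting it at 30.

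Section 9.7.3.1 opens with "To account for confounding by all measured covariates, adjusted analysis will be conducted using propensity score (PS) stratification". It judges balance by a standardised mean difference below 0.1 after trimming and weighting. The only remedy it names for persistent imbalance is interaction terms.

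**The concern.** A single cut at 30 treats all women below it as alike. If gabapentin-exposed and comparator women differ in how they are spread over underweight, normal weight and overweight, nothing in the score acts on that difference directly. The balance check runs on the covariates in the score, so a perfectly balanced obesity indicator can coexist with an imbalance below 30.

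The primary outcomes where this would matter most are SGA, low birth weight and preterm birth, because maternal weight bears on fetal growth. That is a subject-matter judgement; the protocol gives no figure for it. A systematic error of this kind does not shrink when the four countries are pooled.

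**Working it through.** **Comparing the sections.** No stated figure in the protocol depends on how BMI is coded, so there is nothing to reproduce on this point. The relevant texts are:

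- Described: BMI (9.3.3).
- Said to be available: BMI in the birth registers (9.4).
- In the score: obesity yes/no, plus obesity again as a hospital morbidity (9.3.3). The second term adds nothing below BMI 30.
- Checked after weighting: the score's covariates (9.7.3.1), hence obesity but not the categories below it.
- Checked before weighting: crude BMI by exposure group (9.3.3 with 9.7.4.1).

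The gap is therefore in the adjustment and in the balance check after weighting, not in the description.

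**Size, under assumptions.** The protocol gives neither BMI distributions nor BMI risk ratios, so every input here is assumed. The calculation is restricted to BMI below 30, where the obesity indicator is balanced by construction.

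Bias factor = [1 + p1o(RRo − 1) + p1u(RRu − 1)] / [1 + p0o(RRo − 1) + p0u(RRu − 1)]

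Here o is overweight, u is underweight, 1 is gabapentin and 0 is the comparator. The comparator has 25% overweight and 4% underweight throughout.

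| Gabapentin overweight / underweight | RR 1.05 / 1.2 | RR 1.1 / 1.3 | RR 1.2 / 1.5 | RR 1.3 / 1.8 |
|---|---|---|---|---|
| 28% / 4% | 1.0015 | 1.0029 | 1.0056 | 1.0081 |
| 32% / 5% | 1.0054 | 1.0096 | 1.0178 | 1.0262 |
| 38% / 7% | 1.0122 | 1.0212 | 1.0383 | 1.0569 |

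(RR columns: overweight / underweight.) For example, the middle row with 1.2 and 1.5 gives (1 + 0.064 + 0.025) / (1 + 0.050 + 0.020) = 1.089 / 1.070 = 1.018. Ten of the twelve values are at most 1.03.

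The grid places both categories more often in the gabapentin group and lets both raise risk. Exchanging the groups gives the reciprocals, down to 1 / 1.0569 = 0.946, so the direction is not known.

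**Would the balance rule see it?** For a proportion, SMD = (p1 − p0) / √{[p1(1 − p1) + p0(1 − p0)] / 2}. For overweight at 32% versus 25% this is 0.07 / √[(0.2176 + 0.1875) / 2] = 0.07 / 0.450 = 0.16. That exceeds the protocol's 0.1 limit, yet it would not appear because overweight is not in the check. Over the three rows the SMD runs from 0.07 to 0.28 for overweight and from 0.00 to 0.13 for underweight.

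**Against the study's precision.** Table 4 gives 1.223 for preterm birth/SGA against unexposed. With 1,743 exposed, 3,297,080 others and 10% prevalence, the standard error of the log ratio is √[0.9 / 174.3 + 0.9 / 329,708] = 0.0719. Then exp[(1.960 + 0.842) × 0.0719] = 1.223, which reproduces the table. On that scale a bias of 1.03 is ln 1.03 / 0.0719 = 0.0296 / 0.0719 = 0.4 standard errors, and 1.0569 is 0.0553 / 0.0719 = 0.8.

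**The case against.** The strongest reply is that this is a coding preference. The obesity indicator is prespecified and the same in the abstract and the body, and describing a variable more finely than one adjusts for it is no contradiction. Annex 3, said to hold the operational definitions, is not shown. That reply stands as far as calling this an error goes. It does not remove the point, because the list of score covariates is explicit in two places and gives obesity as its BMI term.

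Three stronger readings are tempting, and the documents do not support them.

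- A reader might infer that the opening of section 9.7.3.1 is false because BMI below 30 is measured but left out. The same paragraph defines the score as conditional on the covariates listed in section 9.3.3 and Annex 3. Obesity is the listed covariate, so the statement is not false as written.
- A reader might infer that a birth with neither a recorded BMI nor a hospital diagnosis is coded as not obese. The protocol nowhere says so. The hospital diagnosis may equally be a way to recover obesity where BMI is unrecorded, and a missing-data rule may sit in an analysis plan.
- A reader might infer that usable BMI exists for nearly all births in all four countries. Section 9.4 says the birth registers contain it, but Table 2 names the National Registry of Norway for the row that includes BMI, and no completeness figure is given.

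Two further replies stand in part. Correlated covariates in the score (diabetes, hypertension, smoking, hospital-recorded obesity) may remove some of the difference. And section 9.9 remarks that adjusting for continuous covariates is more complex because a shape must be specified. That remark sits in a paragraph on medication use, and categories need no assumed shape.

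**Conclusion.** The point holds as a cheap improvement. The score carries BMI only as obesity, so differences among underweight, normal-weight and overweight women are not directly adjusted for or checked after weighting.

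The residual bias is probably a factor of about 1.00 to 1.03, up to 1.06 in the most extreme assumed case, in either direction. All of these sizes rest on assumed prevalences and risk ratios. They are small against the Table 4 limit of 1.223 for preterm birth/SGA versus unexposed, and smaller still relative to the 1.243 to 1.289 shown for the active comparators. The bias alone is unlikely to change a conclusion. The reason to act is that the variable is already to be extracted and the better coding costs little.

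**What to change.** In the propensity-score list in section 9.3.3 and the abstract, replace the obesity indicator with BMI categories: below 18.5, 18.5-24.9, 25-29.9, 30 or more, and not recorded. Use a hospital obesity diagnosis to place births without a recorded BMI in the top category. Include every category in the balance table after weighting. State which Norwegian source supplies BMI, so that section 9.4 and Table 2 agree.

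The cost is up to four terms per model in place of one, across the 16 propensity scores in each country, and some sparse cells. At an assumed 4% to 8% underweight, the 374 first-trimester exposed births in Denmark or in Finland (Table 3) would include about 15 to 30 underweight women (0.04 × 374 = 15; 0.08 × 374 = 30).

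Section 9.7.3.1 allows small categories to be collapsed, but on non-convergence it also removes the covariates with the smallest cells one at a time. The text should therefore say that adjacent BMI categories are collapsed first, so that BMI is not dropped.
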